12.3 Concomitant Medication

For interaction with other therapeutic agents and management of concomitant therapies, please refer to the Donepezil hydrochloride Summary of Product Characteristics (Appendix A1 and 2).

The use of other cholinesterase inhibitor medications will be prohibited throughout the study. The use of the N-methyl-d-aspartate antagonist memantine will also be prohibited at study entry and throughout the study.

Stable doses of atypical anti-psychotic medication (i.e. dose unchanged for 6 weeks prior to study entry) *will* be permitted. The use of these agents during the study *will* also be permitted if, in the opinion of the investigator, they are required to manage psychotic symptoms associated with PDD.

No restrictions will be placed upon the use of anti-parkinsonian drugs (other than non-selective centrally acting anticholinergic drugs (as per exclusion criteria), which are contraindicated in people with PD and cognitive impairment, and which may antagonise the action of cholinesterase inhibitors. These are prohibited at study entry and throughout the study.

A complete listing of all concomitant medication (including over the counter medications) received during the treatment phase must be recorded in the relevant CRF.

Patient will be provided with the study specific drug interaction safety card and a medication card to confirm their daily dose at each stage of the study.

13. Randomisation

A blocked allocation system will be used to allocate patients (on a 1:1 ratio) to the two groups (block size will not be disclosed to the investigators). Randomisation will be stratified by site only.

Randomisation will be administered centrally via Newcastle Clinical Trials Unit using a secure password-protected web-based system.

PRIOR TO RANDOMISATION PLEASE ENSURE YOU HAVE COMPLETED THE INCLUSION/EXCLUSION CRF AND THE RANDOMISATION CRF, thus ensuring that the patient is eligible and has the following scores:

ACE-R ≤ 88 Mattis DRS-2 ≤8 but ≥4 Beck Depression Inventory <13

Contact details for Randomisation: http://apps.ncl.ac.uk/random/

(available 24 hours a day)

Randomisation will generate a 4-digit kit number for each participant that links to the corresponding allocated study drug (blinded), in accordance with block size and strata. The kit number must be clearly documented by the investigator on the trial prescription to ensure that the study pharmacist dispenses the correct study medication.

PATIENTS MUST START THEIR STUDY MEDICATION ON THE SAME DAY AS RANDOMISATION.

14. Blinding

Assignment to either active or placebo arm will be blinded to both the participant and investigator/assessor (double-blind) through the use of matched placebo. The assessor at each visit for the Mattis DRS-2, NPI-10 and BADLS will be independent, and thus blinded not only to the treatment arm, but also to reports of general symptoms, progress and adverse events. The latter, in particular, could potentially influence the assessor as to which treatment the participant may be taking.

Code breaking can be achieved by accessing the secure website, http://apps.ncl.ac.uk/random/ via password access. In addition sealed code-break envelopes will be kept in the Central Pharmacy (The Newcastle upon Tyne Hospitals NHS Foundation Trust) and in the pharmacy at participating hospitals; unblinding should only occur in an emergency and the Chief Investigator immediately informed. If the code is broken, details including the participant number, who broke the code, why and when shall be recorded and maintained in the site file. Code breaks will not be routinely made for participants who complete study treatment. Following a code break, should a clinician wish to supply donepezil hydrochloride on an open label prescription basis, this must then be supplied from normal routine pharmacy stock and not from clinical trial supplies.

At the final visit, the integrity of the blind will be assessed by asking both the participants and their treatment assessor: "Do you think you were taking donepezil hydrochloride or the dummy pill? Why do you think this?" The treatment assessor will be asked to record their answers on a separate CRF, prior to asking the participant to avoid bias.

Following the completion of the study treatment, and data analysis, a patient's treatment can be unblinded and information confirming the treatment made available to patients upon request.

15. Study Data

15.1 Assessments / Data Collection

Each study visit should last approximately 3 to 3.5 hours for assessment of both the participant and carer/informant. The exception to this is Visit 1 where the number of assessments including the recording of background information will make this the longest visit.

Visit 1: Screening (-14 days +/- 2 days, e.g. days 12-16)

The following procedures and assessments will be carried out at the screening visit:

- 1. Capacity Assessment
- 2. Informed consent for participant and carer informant
- 3. Nomination of back-up spokesperson and/or Personal Consultee
- 4. Checking that the participant fulfils the UK Queen Square Brain Bank Criteria for PD
- 5. Establishing the nature and temporal sequence of onset of cognitive symptoms in relation to parkinsonism (dementia that develops ≤ 1 year of onset of motor symptoms represents an exclusion criterion as the person would be classified as having Dementia with Lewy Bodies under such circumstances)
- 6. ACE-R (must score ≤ 88)
- 7. If screen positive (≤ 88) on ACE-R, Mattis DRS-2 (must have an age- and education-corrected total score of ≤ 8 but ≥ 4 , to define "mild" dementia)
- 8. Beck Depression Inventory: completed by participant. If score ≥ 13 then exclude on the basis of significant depression, which may be a confounder for cognitive assessments.
- 9. Medical history
 - a. such severe motor disability, or participants so impaired in their activities of daily living from other aspects of their PD, as to render it impossible to accurately assess cognitive and neuropsychiatric function and ability to rate BADLS would represent an exclusion criterion
 - b. unstable ongoing medical co-morbidity (would represent an exclusion criterion)
 - c. neurosurgery for PD (e.g. DBS) within 12 months of the screening visit
- 10. Drug history
 - a. concomitant medications (stable dose of antipsychotic agents *are* permitted providing dose has remained unchanged for previous 6 weeks)
 - b. previous exposure to a cholinesterase inhibitor is an exclusion criterion
 - c. known sensitivity to donepezil hydrochloride or the excipients of donepezil hydrochloride or placebo are exclusion criteria
 - d. current or previous exposure to memantine is an exclusion criterion
 - e. current use of a non-selective centrally acting anticholinergic drug for control of motor symptoms is an exclusion criterion
- 11. Motor sub-section of the new Movement Disorder Society sponsored version of the Unified Parkinson's Disease Rating Scale (UPDRS)
- 12. ECG (conduction defect or bradycardia deemed to be clinically significant by the investigator would represent an exclusion criterion)
- 13. Routine haematology (full blood count, vitamin B12) and biochemical (urea and electrolytes, random blood glucose, thyroid function tests and liver function tests). These tests should be analysed in the site's laboratories.

Visit 2: Baseline (t=0)

The following procedures and assessments will be carried out at the baseline visit:

- 1. Mattis DRS-2
- 2. NPI-10 (administered to caregiver/informant)
- 3. BADLS (administered to the caregiver/informant)
- 4. Modified ADCS-CGIC interview only
- 5. Montreal Cognitive Assessment (MoCA)
- 6. Parkinson's Disease Cognitive Rating Scale (PD-CRS)
- 7. Scales for Outcomes of Parkinson's disease-cognition (SCOPA-cog) (administered to the patient)
- 8. EQ-5D
- 9. DEMQOL and DEMQOL-proxy (latter administered to the caregiver/informant)
- 10. Scale of Quality of Life of Caregivers (administered to the caregiver/informant)
- 11. UPDRS
- 12. Client Service Receipt Inventory (assessing service use over preceding 6 months) (administered to the caregiver/informant)
- 13. Activities-specific Balance Confidence Scale (ABC)
- 14. Provision of falls diaries
- 15. Check concomitant medications
- 16. Randomisation via web-based service
- 17. Dispense study medication along with study drug interaction safety card and medication card
- 18. Patient commences medication (same day as randomisation)

Note: Assessments 1 - 7 must be carried out by an independent rater (that is, an investigator who is unaware of the outcome of the other assessments to be performed at this visit, such as recording of adverse events, which could potentially un-blind the assessor). The participant should be requested not to discuss possible adverse events or interim problems with this rater prior to their assessments being performed.

Note: Ensure an adequate rest break is provided during the visit along with refreshments for the patient and the spokesperson.

Visit 3: Telephone Call (week 8 ± 5 days)

The purpose of this call is to record any adverse events that may have occurred on the study medication (placebo or donepezil hydrochloride 5mg per day) and check concomitant medications. This call will be made by the Study Nurse. If there are no adverse events that are deemed by the study team to be dose-limiting, then the subject will be requested to increase the dose as prescribed to 10mg per day of donepezil hydrochloride or matching placebo. *Ensure the patient records an increase in the dose on the study medication card.*

Visit 4: 26 weeks (± 7 *days*)

The following procedures and assessments will be carried out at this visit:

- 1. Mattis DRS-2
- 2. NPI-10 (administered to caregiver/informant)
- 3. BADLS (administered to caregiver/informant)
- 4. Modified ADCS-CGIC interview and scoring
- 5. Montreal Cognitive Assessment (MoCA)
- 6. Parkinson's Disease Cognitive Rating Scale (PD-CRS)
- 7. SCales for Outcomes of PArkinson's disease-cognition (SCOPA-cog) (administered to patient)
- 8. EQ-5D
- 9. DEMQOL and DEMQOL-proxy (latter administered to caregiver/informant)
- 10. Scale of Quality of Life of Caregivers (administered to caregiver/informant)
- 11. UPDRS
- 12. Client Service Receipt Inventory (assessing service use over preceding 6 months) (administered to caregiver/informant)
- 13. Activities-Specific Balance Confidence Scale (ABC)
- 14. Provision falls diaries
- 15. Review any adverse events
- 16. Check concomitant medications
- 17. Check study medication returned
- 18. Dispense study medication and medication card.

Note: Assessments 1-7 must be carried out by an independent rater (that is, an investigator who is unaware of the outcome of the other assessments to be performed at this visit, such as recording of adverse events, which could potentially un-blind the assessor). The participant should be requested not to discuss possible adverse events or interim problems with this rater prior to their assessments being performed.

Note: Ensure an adequate rest break is provided during the visit along with refreshments for the patient and the spokesperson.

Visit 5: 52 weeks (± 7 *days*)

The following procedures and assessments will be carried out at this visit:

- 1. Capacity Assessment
- 2. Mattis DRS-2
- 3. NPI-10 (administered to caregiver/informant)
- 4. Modified ADCS-CGIC interview and scoring
- 5. Montreal Cognitive Assessment (MoCA)
- 6. Parkinson's Disease Cognitive Rating Scale (PD-CRS)
- 7. SCales for Outcomes of PArkinson's disease-cognition (SCOPA-cog) (administered to patient)
- 8. BADLS (administered to caregiver/informant)
- 9. EQ-5D
- 10. DEMQOL and DEMQOL-proxy (latter administered to caregiver/informant)
- 11. Scale of Quality of Life of Caregivers (administered to caregiver/informant)
- 12. UPDRS
- 13. Client Service Receipt Inventory (assessing service use over preceding 6 months) (administered to caregiver/informant)
- 14. Activities-Specific Balance Confidence Scale (ABC)
- 15. Provision falls diaries
- 16. Review any adverse events
- 17. Haematological and biochemical tests (full blood count, urea and electrolytes, random blood glucose, and liver function tests)
- 18. Check concomitant medications
- 19. Check study medication returned
- 20. Dispense study medication and medication card.

Note: Assessments 2-8 must be carried out by an independent rater (that is, an investigator who is unaware of the outcome of the other assessments to be performed at this visit, such as recording of adverse events, which could potentially un-blind the assessor). The participant should be requested not to discuss possible adverse events or interim problems with this rater prior to their assessments being performed.

Note: Ensure an adequate rest break is provided during the visit along with refreshments for the patient and the spokesperson.

Visit 6: 76 weeks (± 7 *days*)

The following procedures and assessments will be carried out at this visit:

- 1. Mattis DRS-2
- 2. NPI-10 (administered to caregiver/informant)
- 3. BADLS (administered to caregiver/informant)
- 4. Modified ADCS-CGIC interview and scoring
- 5. Montreal Cognitive Assessment (MoCA)
- 6. Parkinson's Disease Cognitive Rating Scale (PD-CRS)
- 7. SCales for Outcomes of PArkinson's disease-cognition (SCOPA-cog) (administered to patient)
- 8. EQ-5D
- 9. DEMQOL and DEMQOL-proxy (latter administered to caregiver/informant)
- 10. Scale of Quality of Life of Caregivers (administered to caregiver/informant)
- 11. UPDRS
- 12. Client Service Receipt Inventory (assessing service use over preceding 6 months) (administered to caregiver/informant)
- 13. Activities-Specific Balance Confidence Scale (ABC)
- 14. Provision falls diaries
- 15. Review any adverse events
- 16. Check concomitant medications
- 17. Check study medication returned
- 18. Dispense study medication and medication card.

Note: Assessments 1-7 must be carried out by an independent rater (that is, an investigator who is unaware of the outcome of the other assessments to be performed at this visit, such as recording of adverse events, which could potentially un-blind the assessor). The participant should be requested not to discuss possible adverse events or interim problems with this rater prior to their assessments being performed.

Note: Ensure an adequate rest break is provided during the visit along with refreshments for the patient and the spokesperson.

Visit 7: End of study - 104 weeks (± 7 days)

The following procedures and assessments will be carried out at this visit:

- 1. Mattis DRS-2
- 2. NPI-10 (administered to caregiver/informant)
- 3. BADLS (administered to caregiver/informant)
- 4. Modified ADCS-CGIC interview and scoring
- 5. Montreal Cognitive Assessment (MoCA)
- 6. Parkinson's Disease Cognitive Rating Scale (PD-CRS)
- 7. SCales for Outcomes of PArkinson's disease-cognition (SCOPA-cog) (administered to patient)
- 8. EQ-5D
- 9. DEMQOL and DEMQOL-proxy (latter administered to caregiver/informant)
- 10. Scale of Quality of Life of Caregivers (administered to caregiver/informant)
- 11. UPDRS
- 12. Client Service Receipt Inventory (assessing service use over preceding 6 months) (administered to caregiver/informant)
- 13. Activities-Specific Balance Confidence Scale (ABC)
- 14. Review any adverse events
- 15. Haematological and biochemical tests, as outlined above for visit 5
- 16. Check concomitant medications
- 17. Check study medication returned.

Note: Assessments 1-7 must be carried out by an independent rater (that is, an investigator who is unaware of the outcome of the other assessments to be performed at this visit, such as recording of adverse events, which could potentially un-blind the assessor). The participant should be requested not to discuss possible adverse events or interim problems with this rater prior to their assessments being performed.

Note: Ensure an adequate rest break is provided during the visit along with refreshments for the patient and the spokesperson.

Note: If a participant withdraws prematurely from the study, the end of study visit procedures and assessments should be attempted at the point of withdrawal.

Visit 8: Telephone Call (week 106 ± 2 days)

The purpose of this call is primarily to record any adverse effects that may have occurred in the two weeks after discontinuation of study medication.

Note: please see section 17.1 with regards to patient compliance and reminder telephone calls.

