12.2 Administration of Study Drug

Study medication will be labelled according to the requirements of Annex 13. All study medication for a particular site will be provided by Piramal to the site pharmacist following site initiation. Study medication will be for use by trial participants only. There will be study-specific prescriptions, and medication will be dispensed by the site pharmacist when the participant attends for their study assessments. Treatment will be taken on an out-patient basis.

Active and placebo study medication will be provided either as 5mg or 10mg capsules. Each participant pack will be presented as bottles in an outer carton.

Weeks 1-26:	5 bottles (5mg) for 5mg or 10 mg dose as directed by team caring for patient. If patient tolerates 5mg dose after 8 weeks then dose to be increased to 2×5 mg. If between week 9 and week 26 patient does not tolerate increased dose, it can be reduced back to 5mg.
Weeks 26-52:	2 bottles (10mg od)
Weeks 52-78:	2 bottles (10mg od)
Weeks 78-104:	2 bottles (10mg od)

The starting dose will be 5mg/day. All participants will be titrated up to 10mg/day after eight weeks. Side effects will be documented by the participant throughout the course of the trial and will be assessed by the clinical team by telephone contact prior to dose escalation from 5mg to 10mg. Any participant reporting significant side effects on 10mg donepezil hydrochloride/day may have their dose decreased back to 5mg/day, for a further two week period prior to attempting to re-escalate to 10mg/day.

A seven-day visit window is allowed for each 26 weekly dispensing visit. Each visit date should be planned from the date of T0, and not the previous visit.

Study medication will be prescribed by a study clinician according to the protocol, and dispensed to the patient or clinical staff according to local pharmacy policy. Patients in possession of their study medication shall return all trial supplies in their original packaging (even if empty) to the Pharmacist every 26 weeks. All returned, or unused, study medication will be stored in Pharmacy until the end of the study, or until the Trial Manager has completed appropriate reconciliation.

Documentation of prescribing, dispensing and return of study medication shall be maintained for study records.

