19.3 Protocol Specifications

For purposes of this protocol

- All non-serious adverse reactions will be recorded at visits 3-7.
- Any serious adverse events will be recorded throughout the duration of the trial until 2 weeks after the trial medication is stopped.
- Serious adverse events exclude any pre-planned hospitalisations not associated with clinical deterioration.
- Serious adverse events exclude routine treatment or monitoring of the studied indication, not associated with any deterioration in condition.
- Serious adverse events exclude elective or scheduled treatment for pre-existing conditions that did not worsen during the study.

19.4 Recording and Reporting Serious Adverse Events or Reactions:

All adverse events should be reported. Depending on the nature of the event, the reporting procedures below should be followed. Any questions concerning adverse event reporting should be directed to the Chief Investigator or MUSTARDD-PD Trial Manager in the first instance. Figure 1 summarises the reporting procedures.

Adverse Event (including Adverse Reaction): All non-serious adverse events / reactions during drug treatment will be reported on the study CRF and sent to Newcastle Clinical Trials Unit within 2 weeks of the form being due. Severity of AEs will be graded on a three-point scale (mild, moderate, or severe – see above). Relation of the AE to the treatment should be assessed by the investigator at site. The individual investigator at each site will be responsible for managing all adverse events / reactions according to local protocols as the study drug is licensed for use in other indications.

Serious Adverse Event / Reaction (SAE/SAR, including SUSARs): All SAEs, SARs and SUSARs during drug treatment will be reported to the Chief Investigator within 24 hours of learning of their occurrence. The initial report can be made by telephone, fax or e-mail. In the case of incomplete information at the time of initial reporting, all appropriate information should be provided as follow-up as soon as this becomes available. Relationship of the SAE to the treatment should be assessed by the investigator at site, as should the expected or unexpected nature of any serious adverse reactions.

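### The post-drug safety call is set at week 106 and not timed from the last dose, so the two weeks it is meant to cover are not guaranteed when Visit 7 is late or drug stops early

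*Protocol*

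**What the plan says.** The last clinic visit is "Visit 7: End of study - 104 weeks (± 7 days" (section 15.1). Its task list includes "Check study medication returned", and no drug is dispensed. The final contact is "Visit 8: Telephone Call (week 106 ± 2 days". The schedule in section 15.2 repeats both timings and shows no contact after Visit 8.

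The call's purpose is stated relative to the end of drug: "The purpose of this call is primarily to record any adverse effects that may have occurred in the two weeks after discontinuation of study medication". Section 19.3 uses the same reference point: "Any serious adverse events will be recorded throughout the duration of the trial until 2 weeks after the trial medication is stopped".

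Section 12.2 says how dates are set: "Each visit date should be planned from the date of T0, and not the previous visit". That sentence directly follows another: "A seven-day visit window is allowed for each 26 weekly dispensing visit". The dosing table in the same section ends at week 104.

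Section 16.1 expects about 50% of participants to stop medication prematurely. Section 17.2 asks them to continue scheduled follow-up. For those who leave the study, section 15.1 asks that end-of-study procedures be attempted when they withdraw.

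**The concern.** The purpose of the call and its date use different clocks. The purpose counts from the end of drug, while the date counts weeks from T0. The two agree only if drug ends close to week 104. A site can keep within both visit windows and still call well before two weeks have passed, and monitoring would have nothing to flag.

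For someone who stops drug early, the week-106 call can come many months after the period it is meant to cover. What is at stake is consistent, active enquiry about adverse effects shortly after the last dose.

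**Working it through.** **Inputs.** Visit 7 is at week 104 ± 7 days and Visit 8 at week 106 ± 2 days (sections 15.1 and 15.2). The target interval is two weeks, or 14 days (sections 15.1 and 19.3).

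**The plan's own figure.** 106 × 7 − 104 × 7 = 742 − 728 = 14 days. The nominal schedule reproduces the intended two weeks.

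**Permitted range.** Visit 7 falls on days 721 to 735 and Visit 8 on days 740 to 744.
- Shortest gap: 740 − 735 = 5 days.
- Longest gap: 744 − 721 = 23 days.

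In general, gap = 14 + d8 − d7, where d7 (−7 to +7) and d8 (−2 to +2) are the deviations from the nominal day.

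| Visit 7 | Gap to Visit 8 (days) |
|---|---|
| 7 days early | 19–23 |
| On time | 12–16 |
| 3 days late | 9–13 |
| 7 days late | 5–9 |

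There are 15 × 5 = 75 permitted day pairs. Of these, 35 give less than 14 days (9 + 8 + 7 + 6 + 5) and 25 give less than 12 (7 + 6 + 5 + 4 + 3). These are counts of pairs, not probabilities.

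**When the gap equals time since last dose.** It does so only if the participant takes drug up to Visit 7. If dosing instead ends at week 104 (day 728), where the section 12.2 table ends, a late Visit 7 does not move the last dose and the call falls 740 − 728 = 12 to 744 − 728 = 16 days after it. The protocol gives neither a last-dose date nor a capsule count, so it does not settle which case applies.

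**Early stop.** Take a stop at week 52 (day 364). The call then falls 740 − 364 = 376 to 744 − 364 = 380 days later. A participant who stays in follow-up is asked about adverse events at the next scheduled visit. The longest nominal interval between visits is week 76 to week 104, which is 28 weeks. For a participant who leaves the study, no contact two weeks later is stated.

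**With the call timed from last dose + 14 ± 2 days.** The interval is 12 to 16 days for every completer.

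**The case against.** The strongest reply is that the schedule works as designed. The nominal gap is exactly two weeks, and an on-time Visit 7 keeps it within two days of that. This stands: a reader might infer that the schedule fails to deliver two weeks, but the documents support only that it does not guarantee them.

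The 5-day figure is also conditional. It needs drug to continue to a Visit 7 held a full week late and the call to be made two days early. The T0 rule in section 12.2 may cover only dispensing visits, and Visit 8 is not one. This stands in part. The week-106 label is itself a count from T0, so the range of 5 to 23 days follows without that rule. The assumption about continued dosing remains open.

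A reader might turn the 35 of 75 pairs into a statement that nearly half of calls come too early. That would require every day in the windows to be equally likely, which nothing supports. It would also count calls at 12 or 13 days, which the protocol's own ± 2 days allows even when Visit 7 is on time.

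A reader might also infer that events after an early call are lost. Section 19.3 requires serious events to be recorded until two weeks after drug stops, whenever the call is made. The shortfall is in active enquiry, chiefly about non-serious effects. For those, section 19.3 lists only visits 3 to 7, although the schedule marks adverse events at Visit 8. Nor are early stoppers without follow-up: those who stay have adverse events reviewed at each later visit.

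**Conclusion.** The point holds as a minor defect in safety ascertainment. The call's date is not tied to the event that defines its purpose. For completers, the permitted gap from Visit 7 is 5 to 23 days around a correct nominal 14. It falls short when Visit 7 is late, on the assumption that drug is taken until that visit. If dosing ends at week 104 regardless, the call falls 12 to 16 days after the last dose and completers are not affected.

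For the roughly 50% expected to stop early, the mismatch does not depend on that assumption: week 106 has no relation to their stop date. Those still followed are asked at the next scheduled visit, and those who leave have no stated contact at two weeks. No primary outcome, power calculation or efficacy comparison is affected.

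**What to change.** Reconcile sections 12.2, 15.1, 15.2 and 19.3:
- Time the post-drug call from the recorded date of last dose, for example last dose + 14 days with the existing ± 2 days. A window that opens only at day 14 is a possible preference but is not needed to cure the mismatch.
- Record the last-dose date explicitly.
- State that planning from T0 does not apply to this call.
- State whether the same call is made after an early stop, both for those who stay in follow-up and for those who leave.
- Make section 19.3 agree with the schedule on whether non-serious effects are recorded at Visit 8.

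The cost is a wording change and a revised schedule entry. Completers have no extra contact. If the call is applied to early stoppers, each gets one short additional telephone call. At the expected rate that is up to about 0.5 × 500 = 250 calls over the trial.
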